### **Subject Replacement**

Subjects who prematurely discontinue from the study or become ineligible will not be replaced once they have been randomized. Every effort will be made to obtain follow-up data on all participants randomized.

## **8 Statistical Plan**

### **8.1 Sample Size and Power Determination**

The power calculation is based on current standards in exploratory neuroimaging studies. Previous fMRI studies that used groups of 15 subjects per condition were sufficient to detect significant differences in BOLD signal response to behavioral tasks. Due to resource limitations, our sample size will be limited. The sample size will allow us to detect effect sizes of 0.93 or larger in BOLD signal between groups with 80% power controlling for type 1 errors at 5% using a one-sided test.

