### 2.1 Primary Objective

**Aim 1:** Compare differences between the CBT and WL groups at week 16 in changes in BOLD fMRI response to the food-specific SST.

Hypothesis 1: Since CBT for BED involves successful management of dietary disinhibition, we propose that participants will have favorable pre- to post-treatment changes in regions of interest (ROIs) that are associated with inhibitory control. We hypothesize that the CBT group, compared with the WL group, will have increased activation in the PFC, IFG, OFC, and insula during the food-specific SST.

**Aim 2:** Compare differences between the CBT and WL groups at week 16 in changes in BOLD fMRI response to recall of binge foods (i.e., script-driven imagery).

Hypothesis 2: CBT teaches participants how to reduce responsiveness to binge foods. Thus, we propose that CBT will alter neural responses in regions that promote food reward. We hypothesize that after treatment, the CBT group, compared to the WL group, will have decreased activation in the PFC, OFC, insula, VTA, and VS in response to script-driven imagery of binge foods.

**Aim 3:** Determine whether pre-treatment neural activation on the SST and script-driven imagery task predict differences between CBT responders and non-responders ( $\geq 1$  binge eating episode in the past 28 days).

Hypothesis 3: Results from other psychiatric disorders show that patients with greater dysfunction in neural circuitry related to their disease are less likely to respond to treatment. We predict that relative to CBT responders, non-responders will have lower pre-treatment BOLD activation in the inhibitory control ROIs during the SST and higher pre-treatment BOLD activation in the reward ROIs during the script-driven imagery task.

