## 2.2 Secondary Objectives

**Aim 4:** Assess the associations between pre- to post-treatment behavioral changes in reported binge eating episodes (percent reduction and categorical response), in reward-based eating drive, and in dietary inhibition, and pre- to post-treatment neural changes on the SST and script-driven imagery task.

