## 6 Procedures

### 6.1 Recruitment, accrual, and retention.

We will recruit participants at a single site – the Center for Weight and Eating Disorders at the University of Pennsylvania, Philadelphia, PA, USA - through local media advertisements and news shows/outlets, as well as Internet-based advertising outlets and flyers and brochures around our community. We also will advertise using clinician referrals from primary care clinics affiliated with the University of Pennsylvania Health System. We will be recruiting from the university-based website, iConnect, which allows access to their volunteer registry data of potential participants. We will use study condition terms such as “binge eat\*”; “eating disorder\*”; and/or obesity. Recruitment may also use Penn media services (e.g., communications) and social media (e.g., Facebook, Twitter; please see attached for information about Facebook recruitment). We conservatively estimate a drop-out rate of 25% based on prior experience in our labs and will enroll 40 participants to have 30 complete the study. Based on prior studies of BED in our labs, we expect to screen 50 to 75 females who respond to our advertisements per month and enroll about 5 females each month. To minimize attrition we will use multiple evidence-based strategies that improve retention rates including scheduling sessions at convenient times, maintaining close contact, and providing compensation for assessment visits and travel costs. Travel compensation will be given at the end of each CBT session, as applicable. Our research group has successfully completed a number of long-term intervention and fMRI trials that have lasted >4 months with attrition rates <20%.

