#### **8.2.2 Efficacy Analysis**

Baseline to 16-week changes self-report and behavioral variables will be examined using mixed-effect general linear models, fit with the between-subject factor of treatment group and the within-subject factor of time. Differences between groups in percent of participants classified as responders will be analyzed using a chi-square test. Statistical significance will be defined as  $p < 0.05$  in analyses.

The primary analysis will only include responses to high calorie food, since the CBT intervention is designed to improve inhibition to “bad” (i.e., high-calorie) foods. Response-inhibition-related BOLD activity will be tested using similar analytic strategies as previous trials. Analysis of data indicating changes in each ROI will be conducted using a mixed-effects general linear model with time (baseline vs 16 weeks) and trial type (stop vs go) as within-subject factors and group (CBT vs WL) as a between-subjects factor. *Percent reduction in binge eating episodes will be included as a statistical covariate.* Since no significant differences have been found between successful vs unsuccessful stops, we will not distinguish these *a priori*. Exploratory contrasts will be conducted using the same analysis procedures to examine specificity to energy density (contrast with high- and low-calorie foods) and general inhibitory behavior (high-calorie food vs neutral and low-calorie food vs neutral). We will also examine differences among the CBT and WL groups in brain-behavior correlations using correlations between BOLD activation in the ROIs with the behavioral measure (SSRT).

The primary analysis for aim 2 will be the script-listening time-block. We will use a similar approach as above to examine data from recall of binge eating episodes. In the mixed-effects general linear model, analysis of data indicating changes in each ROI will be conducted using time (baseline vs 16 weeks) and trial type (binge food vs neutral) as within-subject factors and

group (CBT vs WL) as a between-subjects factor. Percent reduction in binge eating episodes will be included as a statistical covariate.

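### Does section 8.2.2 need to state sidedness for the primary ROI tests, given that the 0.93 detectable effect in section 8.1 rests on a one-sided 5% test?

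*Combined protocol and SAP*

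**What the plan says.** Section 8.1 gives a detectable effect of "0.93 or larger in BOLD signal between groups with 80% power controlling for type 1 errors at 5% using a one-sided test". It does not attach a sample size to that figure, but it cites earlier imaging studies with 15 subjects per condition. Section 6.1 expects 25% drop-out and "will enroll 40 participants to have 30 complete the study", which at 1:1 allocation is 15 per arm.

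Section 8.2.2 begins its significance rule with "Statistical significance will be defined as" and sets it at p<0.05. The rule carries no sidedness, and the two BOLD paragraphs that follow give no alpha of their own. The same section also covers a responder comparison ("Differences between groups in percent of participants classified as responders will be analyzed using a chi-square test") and secondary imaging contrasts ("Exploratory contrasts will be conducted using the same analysis procedures to examine specificity to energy density").

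Section 2.1 states directions. For the stop signal task, the CBT group relative to waitlist "will have increased activation in the PFC, IFG, OFC, and insula during the food-specific SST". For imagery, it "will have decreased activation in the PFC, OFC, insula, VTA, and VS in response to script-driven imagery of binge foods". Section 3.1.1 names the BOLD changes on these two tasks as the primary endpoints. The Aim 4 objective in section 2.2 is non-directional: "Assess the associations between pre- to post-treatment behavioral changes in reported binge eating episodes".

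**The concern.** A power statement describes the planned analysis only if both use the same test. One-sided testing appears once, in the sample size section, and the analysis section does not repeat it. The p<0.05 rule also covers tests for which no direction is given (the responder chi-square, the energy-density contrasts, the Aim 4 associations), so one-sided testing cannot be meant for everything under that rule. A reader has to work out where it applies.

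The directions also differ by task. PFC, OFC and insula are expected to rise on the stop signal task and fall during imagery. A mixed model is often reported with F tests, which carry no direction.

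Sidedness sets the cut-off for each primary ROI. If it were truly open, a result of moderate size in the predicted direction could be called significant or not according to a choice made after the data were seen. The 80% power claim would hold under only one of the two choices.

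**Working it through.** **Inputs.** Enrolment 40 and drop-out 25% (section 6.1): 40 × 0.75 = 30 completers. Allocation 1:1 (section 6.2.3): 15 per arm. Power 80%, alpha 5%, one-sided (section 8.1). The 15 per arm is an inference, supported by the fact that it reproduces the plan's figure.

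**Method.** Two-sample t-test on change in one ROI, with df = 15 + 15 − 2 = 28. The noncentrality parameter is d × √(15/2) = 2.739d. The smallest significant observed difference in SD units is t_crit × √(2/15) = 0.365 × t_crit.

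**The plan's own figure (one-sided 5%).**
- t_crit = 1.701
- effect detectable with 80% power: d = 0.931, matching the stated 0.93
- power at d = 0.93: 79.9%
- smallest significant observed difference: 1.701 × 0.365 = 0.62 SD

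**The alternative (two-sided 5%).**
- t_crit = 2.048
- effect detectable with 80% power: d = 1.060
- power at d = 0.93: 69.1%
- smallest significant observed difference: 2.048 × 0.365 = 0.75 SD

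**Gap between the two.** If the true effect is 0.93, 79.9% − 69.1% = 10.8% of results fall between 0.62 and 0.75 SD, where the verdict depends on sidedness. These cut-offs belong to the simple t-test, not to the planned mixed model with its covariate.

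**Which test does the plan specify?** Set the sections side by side:

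| Question | Where answered | Answer |
|---|---|---|
| Which comparison is tested one-sided? | 8.1 | BOLD signal between groups |
| Is that the primary endpoint? | 3.1.1 | Yes, for both tasks |
| In which direction? | 2.1 | Increase on the stop signal task, decrease on imagery, with the regions listed |
| At what level? | 8.1 and 8.2.2 | 5% in both |
| Is two-sided testing proposed anywhere? | Nowhere | No |

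The pieces needed for a one-sided ROI test (comparison, direction, level) are all present and do not conflict.

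**Does the model permit a one-sided test?** Section 8.2.2 crosses group, time and trial type, each with two levels. Their three-way interaction therefore has (2−1)(2−1)(2−1) = 1 numerator degree of freedom. Its F statistic is the square of a t statistic with a sign, so the one-sided test in the section 2.1 direction can be read from the same fit.

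**The case for a change.** The strongest case for a change is that these are primary endpoints, the plan should fix the cut-off before data are seen, and one sentence would do it. It is true that section 8.2.2 is silent and that a reader must go to sections 8.1 and 2.1 for the answer. It is also true that a one-sided rule needs a direction for each contrast, and section 8.2.2 lists none.

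Less stands beyond that. The directions are in section 2.1, region by region. The responder chi-square, the energy-density contrasts and the Aim 4 associations do not bear on the primary tests: no power claim depends on them, and the one-sided statement is confined to between-group BOLD signal. Ordinary practice is to test them without direction.

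One could also argue that an analyst might use the one-sided cut-off in the predicted direction and still declare opposite changes at the two-sided cut-off, for 5% + 2.5% = 7.5% error per ROI. Nothing in the document proposes this.

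An analyst who overlooked section 8.1 and tested two-sided would face a 2.5% error rate in the predicted direction, not an inflated one. The cost would be power (69.1% rather than 79.9% at 0.93), not false positives.

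**Conclusion.** No change to the plan is needed. The detectable effect of 0.93 is correct for 15 completers per arm and a one-sided 5% test. Sections 8.1, 2.1 and 3.1.1 together make the primary ROI contrasts one-sided at 5% in the stated directions. Section 8.2.2 sets the same 5% level and says nothing against this. The gap is one of cross-reference, which analysts can fill from the same document. Repeating the rule in section 8.2.2 would be tidy but would alter no test, sample size or power figure.

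The difference of 1.06 against 0.93, or 69.1% against 79.9% power, arises only if the team tests two-sided, which the document does not suggest.

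This conclusion rests on 15 evaluable participants per arm. If all 40 gave usable scans (20 per arm), the detectable effect would be 0.80 one-sided and 0.91 two-sided, so 0.93 would be within reach either way. That would require no drop-out, against the plan's own 25%. The calculation covers a single ROI and does not model the covariate or the number of regions tested.

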### **8.2 Statistical Methods**

#### **8.2.1 Baseline Data**

Baseline and demographic characteristics will be summarized by standard descriptive statistics (including mean and standard deviation for continuous variables such as age and standard percentages for categorical variables such as gender).

#### **8.2.2 Efficacy Analysis**

Baseline to 16-week changes self-report and behavioral variables will be examined using mixed-effect general linear models, fit with the between-subject factor of treatment group and the within-subject factor of time. Differences between groups in percent of participants classified as responders will be analyzed using a chi-square test. Statistical significance will be defined as  $p < 0.05$  in analyses.

The primary analysis will only include responses to high calorie food, since the CBT intervention is designed to improve inhibition to “bad” (i.e., high-calorie) foods. Response-inhibition-related BOLD activity will be tested using similar analytic strategies as previous trials. Analysis of data indicating changes in each ROI will be conducted using a mixed-effects general linear model with time (baseline vs 16 weeks) and trial type (stop vs go) as within-subject factors and group (CBT vs WL) as a between-subjects factor. *Percent reduction in binge eating episodes will be included as a statistical covariate.* Since no significant differences have been found between successful vs unsuccessful stops, we will not distinguish these *a priori*. Exploratory contrasts will be conducted using the same analysis procedures to examine specificity to energy density (contrast with high- and low-calorie foods) and general inhibitory behavior (high-calorie food vs neutral and low-calorie food vs neutral). We will also examine differences among the CBT and WL groups in brain-behavior correlations using correlations between BOLD activation in the ROIs with the behavioral measure (SSRT).

The primary analysis for aim 2 will be the script-listening time-block. We will use a similar approach as above to examine data from recall of binge eating episodes. In the mixed-effects general linear model, analysis of data indicating changes in each ROI will be conducted using time (baseline vs 16 weeks) and trial type (binge food vs neutral) as within-subject factors and

group (CBT vs WL) as a between-subjects factor. Percent reduction in binge eating episodes will be included as a statistical covariate.

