## 3 Study Endpoints

### 3.1.1 Primary Study Endpoints

The primary endpoints are baseline to 16-week changes in BOLD fMRI response to food-specific SST and to binge-eating script-driven imagery.

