### 6.2.3 Allocation to Interventional Group

Subjects who meet eligibility criteria and complete their baseline assessment visit will be randomly assigned to the intervention or waitlist condition. We will use a permuted randomized block design that randomly mixes blocks of different sizes (2 to 6) to assign 40 eligible participants to CBT or waitlist conditions using a one-to-one allocation ratio. This randomization design was selected due to the need to create exactly the same group sizes with a small sample. A statistician will conduct the randomization using a computer-generated algorithm.

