### 8.3 Subject Population(s) for Analysis

We will use an intention-to-treat approach of all randomized participants for all primary analyses. Additional analyses will be conducted with protocol-compliant participants.

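### An improvement, not an error: adjusting the primary BOLD tests for the baseline contrast, without the percent-reduction covariate, is usually more precise than the planned group-by-time test

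*Combined protocol and SAP*

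**What the plan says.** Section 3.1.1 defines the endpoints as changes: "The primary endpoints are baseline to 16-week changes in BOLD fMRI response to food-specific SST and to binge-eating script-driven imagery". Section 8.2.2 specifies the aim 1 model for each ROI as a "mixed-effects general linear model with time (baseline vs 16 weeks) and trial type (stop vs go) as within-subject factors", with group as the between-subjects factor. The aim 2 model uses "time (baseline vs 16 weeks) and trial type (binge food vs neutral) as within-subject factors", again with group between subjects. For both it adds: "Percent reduction in binge eating episodes will be included as a statistical covariate". It names no baseline BOLD covariate, no equal-baseline constraint and no covariance structure.

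Four other places bear on the point.
- Section 6.2.3 puts randomization after the baseline scan: "Subjects who meet eligibility criteria and complete their baseline assessment visit will be randomly assigned".
- Section 6.1 "will enroll 40 participants to have 30 complete the study".
- Section 8.3 takes an "intention-to-treat approach of all randomized participants for all primary analyses".
- Section 8.1 concedes: "Due to resource limitations, our sample size will be limited".

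**The concern.** When the baseline scan is a level of time, each arm on the ordinary reading has its own freely estimated baseline mean. The group-by-time contrast is then in essence a difference in mean change. It carries the full noise of the baseline scan, however weakly that scan predicts week 16.

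Because the baseline scan comes before randomization, the two arms share the same expected baseline. A model that uses this fact, by ANCOVA or by constraining the baseline means to be equal, weights the baseline scan by how well it predicts week 16. The target does not change: with equal baseline means, the week-16 arm difference is also the arm difference in change.

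At stake is precision in a trial that expects 30 completers and says its size is set by resources. The scans needed are already planned.

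**Working it through.** **Inputs.** 40 randomized 1:1 (Section 6.2.3), so 20 per arm; 30 completers (Section 6.1), so 15 per arm; 80% power, one-sided 5%, detectable effect 0.93 (Section 8.1). The correlation r is between the baseline and week-16 within-scan contrasts (stop minus go; binge minus neutral), not between raw BOLD values. It appears nowhere in the documents and is shown as a range. Equal variances at both scans (set to 1) and dropout at random are further assumptions.

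**Step 1: the plan's own figure.** A two-sample t test with 15 per arm, 28 df and noncentrality d/√(2/15) reaches 80% power, one-sided 5%, at d = 0.931. This reproduces the stated 0.93. Section 8.1 does not say which SD is the unit.

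**Step 2: variances without the percent-reduction covariate.**
- Baseline-adjusted: V_adj = (1−r²)(2/15)(27/26). The factor 27/26 is (N−3)/(N−4) with N = 30, the cost of estimating the slope.
- Unconstrained group-by-time model using all 20 baselines per arm: V_unc = 2(1−r)²/20 + (1−r²)[2/15 + 2(1/15−1/20)/26].
- Completer change score: V_chg = 4(1−r)/15.

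At r = 0.5: V_adj = 0.75 × 0.1333 × 1.0385 = 0.1038. V_unc = 0.0250 + 0.75 × 0.1346 = 0.1260, ratio 1.213. V_chg = 0.1333, ratio 1.284.

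| r | V_unc/V_adj | V_chg/V_adj | Power of the adjusted test where the unconstrained one has 80% |
|---|---|---|---|
| 0.3 | 1.361 | 1.481 | 89% |
| 0.5 | 1.213 | 1.284 | 86% |
| 0.7 | 1.100 | 1.133 | 83% |
| 0.8 | 1.052 | 1.070 | 82% |
| 0.9 | 1.010 | 1.014 | 80% |
| 0.95 | 0.991 | 0.988 | 80% |

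A simulation with 200,000 replicates per r gave 1.360, 1.218, 1.101, 1.052, 1.012 and 0.991 for the middle column. Mean null estimates were within 0.0011 of zero.

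**Step 3: break-even and worst case.** V_chg/V_adj = [2/(1+r)](26/27), which equals 1 at r = 25/27 = 0.926. V_unc/V_adj equals 1 at the same r. With 40 completers the factor is 37/36 and break-even is 35/37 = 0.946. As r approaches 1 the two ratios tend to 0.972 and 0.963. Adjustment then costs at most 2.9% more variance than the unconstrained model and 3.8% more than the completer change score.

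**Step 4: what the percent-reduction covariate does.** Percent reduction was added as a main effect to two-scan models of the contrast, in simulations with 15 per arm, complete data and no treatment effect. Assumed mean reductions were 79% in CBT (the midpoint of the 68–90% in Section 7) and 10% on the waitlist, both with SD 25%.
- The excess variance of the unconstrained over the equal-baseline model fell to about 10–17%, 7% and 4% at r = 0.3, 0.5 and 0.7. With complete data and no covariate it is 48%, 28% and 13%.
- With baseline BOLD correlated 0.3 to 0.5 with reduction in the CBT arm only, the equal-baseline estimate at r = 0.3 was biased by about −0.07 to −0.15 SD. The planned contrast stayed within about 0.01 of zero.
- Completer ANCOVA plus the covariate no longer matched the equal-baseline model, and had more than twice the variance of the planned contrast.

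**Step 5: equivalence and calibration without the covariate.** With 5 baseline-only participants per arm, the equal-baseline model and completer ANCOVA gave the same arm estimate (largest difference 7 × 10⁻⁸). One-sided 5% type I error was 4.9–5.1% for the ANCOVA t test but 6.8–7.0% for a large-sample Wald test from maximum likelihood. The longitudinal form therefore needs a small-sample method.

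**The case against.** The strongest objection is that the planned analysis is sound and matches the endpoint, so this is a preference. It is indeed sound. A reader might infer that the planned test is biased or invalid because it ignores chance baseline imbalance; the documents do not support that. Under randomization the contrast is unbiased for the same arm difference.

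A second objection is that the percent-reduction covariate undoes the argument, and this one stands. Randomization equalizes the arms' expected baselines overall, not conditionally on a variable measured later. Hypothesis 3 in Section 2.1 itself predicts that baseline activation differs by response to CBT. A reader might infer that one can add the baseline constraint and settle the covariate later; Step 4 shows that this does not hold. In fairness, with a covariate-by-time term the constrained model was again unbiased and more precise, and the unconstrained one was biased. Section 8.2.2 mentions no such term.

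Third, the size rests on an r that nobody has stated, and above break-even the direction reverses. This also stands, although the two sides are unequal: 36% at r = 0.3 against at most 2.9%.

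Two further inferences should be avoided. Protection against chance imbalance is not a second benefit. The baseline mean difference has SD √(2/20) = 0.316, and an imbalance of that size moves the unconstrained estimate by (1−r) × 0.316, or 0.16 at r = 0.5. Squared, that is exactly the first term of V_unc. And the break-even correlation of about 0.93 has nothing to do with the 0.93 effect size in Section 8.1.

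**Conclusion.** The point holds as a low-cost improvement to Section 8.2.2, not as an error. Adjusting for the baseline contrast is more precise than the planned structure when r is below about 0.926 with 30 completers (0.946 with 40). The planned structure's excess variance is about 36%, 21%, 10% and 1% at r = 0.3, 0.5, 0.7 and 0.9, so the gain is material at low to moderate r and negligible from about 0.9. If the 0.93 in Section 8.1 is in change-score SDs, which it does not say, the detectable effect becomes 0.765, 0.822 and 0.875 at r = 0.3, 0.5 and 0.7.

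These figures assume equal variances at the two scans, dropout at random, 15 completers per arm and no percent-reduction covariate. The last is a condition of the recommendation as well as an assumption of the arithmetic. Confidence is medium, because r is unknown.

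**What to change.** In Section 8.2.2:
- For each ROI, form the within-scan contrast: stop minus go for high-calorie food, and binge minus neutral during script listening.
- Make the primary test the week-16 arm difference adjusted for the baseline contrast. Use either ANCOVA or the equivalent longitudinal model with equal baseline means, unstructured covariance and a small-sample method such as Kenward-Roger. Name one of the two as primary. With only a random subject intercept, the contrast is treated as uncorrelated across scans and the gain is not secured.
- Fit this test without percent reduction in binge episodes, and move that covariate to a secondary or mechanistic model. This also means that a participant without week-16 binge data is not dropped from the primary model for lack of a covariate value.
- Keep the planned group-by-time model as a sensitivity analysis.

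The longitudinal form keeps baseline-only participants in the model, in line with Section 8.3, although they do not change the arm estimate. The cost is the rewording, one degree of freedom, one more labelled set of results to report, and at most about 3% more variance than the unconstrained model (4% against a completer change score) if r is close to 1. No new scans, visits or participants are needed.

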### 3.1.2 Secondary Study Endpoints

Secondary study endpoints include changes in binge eating episodes (percent reduction and categorical response), in reward-based eating drive, and in dietary inhibition.

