## 7 Study Interventions

**CBT Intervention.** The CBT intervention (Table 1) will consist of weekly, 50-minute individual meetings for 16 weeks with a clinician trained in CBT for binge eating disorder. The treatment will be administered using a manualized treatment protocol adapted from Fairburn and Mitchell. The overall goals of CBT for BED are to interrupt binge-eating behavior, learn self-management strategies to help reinstitute more normal eating habits, change erroneous beliefs about weight and shape and develop healthier attitudes towards one's body. Participants are taught a variety of skills including identifying triggers of binge eating episodes, correcting beliefs or thought patterns related to binge eating, and altering attitudes regarding food and eating. Homework is assigned at each session so participants can practice the skills that they have learned. To monitor treatment integrity and adherence, treatment sessions will be reviewed under the supervision of Drs. [name] or [name]. This treatment has been tested in a number of trials for BED and we anticipate seeing 50% of individuals with full remission from binge eating and a 68-90% reduction in the number of binge eating episodes.

Table 1. CBT for BED Intervention

Stage	Aim	Weeks
1: Introduction	Jointly creating a formulation of the processes maintaining the eating disorder Establish real-time monitoring of eating and other relevant thoughts and behavior Provide education about body weight regulation and fluctuations, the physical complications and the adverse effects of dieting Introduce weekly weighing Introduce a pattern of regular eating	1-4
2: Transition	Jointly reviewing progress Identify barriers to change Modify the formulation as needed	5-6

	Plan Stage Three	
3: Main body of treatment	Address key mechanisms that are maintaining BED Overevaluation of shape and weight - Provide education about overevaluation and its consequences - Reduce unhelpful body checking and avoidance - Relabel unhelpful thoughts or feelings such as “feeling fat” - Develop previously marginalized domains of self-evaluation - Explore the origins of the overevaluation Dietary restraint - Change inflexible dietary rules into flexible guidelines - Introduce previously avoided food Event triggered changes in eating - Develop problem-solving skills to directly tackle such events - Develop skills to accept and modulate intense moods	7-14

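### Both primary models include percent reduction in binge eating, a post-randomization secondary endpoint, without saying how it enters; it is inert on the plainest reading and changes the question if it acts on the tested contrast

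*Combined protocol and SAP*

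**What the plan says.** Section 2.1 sets Aim 1 as "Compare differences between the CBT and WL groups at week 16 in changes in BOLD fMRI response to the food-specific SST"; Aim 2 asks the same of the script-driven imagery task. Section 3.1.1 agrees: "The primary endpoints are baseline to 16-week changes in BOLD fMRI response to food-specific SST and to binge-eating script-driven imagery". Neither conditions on how much binge eating fell.

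For Aim 1, section 8.2.2 states "Analysis of data indicating changes in each ROI will be conducted using a mixed-effects general linear model". Treatment arm is compared between participants, and the repeated factors are listed as "time (baseline vs 16 weeks) and trial type (stop vs go) as within-subject factors". The section then adds "Percent reduction in binge eating episodes will be included as a statistical covariate". The Aim 2 model has the same structure, with binge food versus neutral as trial type, and repeats the sentence. No interaction, coding or centring of the covariate is given, and no term is named as the primary test.

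Section 3.1.2 lists the same variable as an outcome: "Secondary study endpoints include changes in binge eating episodes (percent reduction and categorical response". Section 7 anticipates "a 68-90% reduction in the number of binge eating episodes" with CBT. Under section 6.2.3, randomization follows the baseline visit, so percent reduction to week 16 is a post-randomization variable. Section 2.2 (Aim 4) already covers the association between binge change and neural change. Section 8.3 calls for intention-to-treat analysis of everyone randomized.

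**The concern.** Adjusting a treatment comparison for something the treatment changes generally alters what is estimated. If CBT changes BOLD response partly by the same route that reduces binge eating, the adjusted group term removes that part. The remainder is a direct effect only if nothing unmeasured drives both binge change and BOLD change. Otherwise it can be biased in either direction. No section states a direct-effect or mediation question for Aims 1 and 2.

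Because the way of entry and the tested term are both open, two analysts could follow section 8.2.2 and report different primary effects, only one of which answers the aims. The covariate also needs a week-16 binge count, which not every randomized participant will have.

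**Working it through.** **1. The plan's own power figure.** Section 8.1 gives an effect of 0.93, 80% power and one-sided 5%. Section 6.1 plans 40 enrolled and 30 completing, so 15 per arm at 1:1. For a two-sample t test, the noncentrality is 0.93 × √(15/2) = 2.547 on 28 df, and power is 79.9%. The stated figure is reproduced, for an analysis without the covariate.

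**2. Does the way of entry matter?** Mixed models were fitted to one balanced simulated data set (2 groups × 2 times × 2 trial types). Estimates, with SE in brackets:

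| Covariate form | Group × time (averaged over trial type) | Group × time × trial type |
|---|---|---|
| None | 0.805 (0.251) | 1.176 (0.501) |
| Main effect | 0.805 (0.251) | 1.176 (0.501) |
| Zero at baseline, its value at week 16 | 0.554 (0.297) | 1.176 (0.494) |
| Crossed with time | 0.458 (0.314) | 1.176 (0.495) |
| Crossed with time and trial type | 0.458 (0.305) | 0.201 (0.609) |

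A value that is constant within a participant cancels from any within-participant contrast, so a main effect changes nothing. A term crossed with the tested contrast does not cancel. Analysing a stop-minus-go change score with the covariate is equivalent to the last row for the three-way term.

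**3. Precision where the tested term is affected.** Let d = (CBT mean − waitlist mean)/SD of percent reduction. With equal arms, the variance inflation is 1 + d²/4. The CBT mean of 68 to 90% is section 7's range, treated as an arm mean. The waitlist mean (0 to 40%) and within-arm SD (30 to 50 points) are assumptions, because the documents give neither. Nothing is mediated, and the covariate is unrelated to BOLD change within arms.

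- Least separated: d = (68 − 40)/50 = 0.56; inflation 1.08; noncentrality 2.547/√1.08 = 2.45 on 27 df; power 77%.
- Most separated: d = (90 − 0)/30 = 3.0; inflation 3.25; noncentrality 2.547/√3.25 = 1.41; power 39%.

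The effect detectable with 80% power becomes 0.97 to 1.68. Precision would improve only if the within-arm correlation with BOLD change exceeded √(1 − 1/inflation), which is 0.27 to 0.83.

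**4. Estimate where the tested term is affected.** If a share m of the effect runs through binge reduction, the adjusted term has expectation (1 − m) × 0.93. At m = 0.5 that is 0.465, about 0.47, for 79% versus 20% and SD 30. The expectation does not depend on the SD; at SD 35, simulation also gave 0.47, with 25% power.

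With a shared cause and no mediation, the expectation is 0.93 − r × d, where r is the within-arm correlation and BOLD change is scored in the hypothesized direction. For d from 0.56 to 3.0, it is 0.82 down to 0.33 at r = +0.2, and 1.04 up to 1.53 at r = −0.2.

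**5. Missing covariate values.** Section 6.1 plans for 25% dropout: 0.25 × 40 = 10 participants. Table 2 schedules the Eating Disorder Examination and the scan at the same visit (T2), so most participants without a week-16 binge count would also lack the week-16 scan. What the covariate additionally removes is mainly their baseline scans.

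**The case against.** The strongest reply is that nothing is distorted on the plainest reading. Section 8.2.2 lists time and trial type as factors and adds a covariate with no interaction; step 2 shows that this leaves both candidate terms unchanged when data are complete. That stands. A reader might infer that the primary tests are biased as written, and the documents do not support this: every power and bias figure above needs a crossing, recoding or change score that the plan does not state. Those forms remain open to an analyst because the text also speaks of data indicating changes, says "Response-inhibition-related BOLD activity will be tested using similar analytic strategies as previous trials", and names no tested term.

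A reader might also infer that no form of the covariate could be useful. That is too strong. Centred within each arm and crossed with the contrast, it keeps the full 0.93, with simulated power of 80 to 87% depending on the mediated share. The plan mentions no such centring.

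A third tempting reading is that the covariate costs 10 of 40 participants, or biases the result through dropout. The 10 is planned visit dropout, and section 8.1's figure already rests on 15 per arm. Material bias from losing baseline-only participants needs a selective dropout mechanism that no section describes. The tension with section 8.3 is real but limited.

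Finally, the magnitudes are illustrative. Percent reduction cannot exceed 100, and section 7 expects half of participants to reach full remission, so a normal covariate is only a rough approximation.

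**Conclusion.** The point holds as an unspecified post-randomization covariate in both primary models. With complete data it is inert as a main effect. If it acts on the tested contrast without centring within arm, it replaces the CBT-versus-waitlist difference with one conditional on equal binge reduction. In that case only, power at 0.93 is about 39 to 77% instead of 80% with nothing mediated, and the expected estimate is about 0.47 with half the effect mediated. The waitlist mean, SD, mediated share and shared-cause correlation are assumptions; they set the size of the change, not whether the question changes. Under every form, a missing week-16 count without imputation removes a randomized participant from an analysis described as intention-to-treat, mainly at the cost of her baseline scan. This goes beyond missing detail: the plan states an analysis rule that brings Aim 4's question into the primary models without serving Aims 1 and 2.

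**What to change.** 1. Delete the covariate sentence from both primary models and make the models without it primary.
2. Name the tested contrast for each aim, for example group × time × trial type (stop versus go for Aim 1, binge versus neutral for Aim 2).
3. Fit by likelihood to all available scans and state the missing-at-random assumption.
4. Use percent reduction only in Aim 4, for which section 8.2.2 gives no model, alongside the other measures in section 2.2 (categorical response, reward-based eating drive, dietary inhibition). Keep arm in the model, and report the result as an association or as labelled exploratory mediation.
5. Optionally, if a symptom covariate is wanted in the primary model, use binge frequency from the screening Eating Disorder Examination, which precedes randomization, and enter it so that it can act on the tested contrast. If it is unrelated to BOLD change, this costs about one point of power (78.6% against 79.9%).

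The cost is two sentences deleted and about four added. No new data or visits are needed, since the Eating Disorder Examination is already scheduled at screening and T2.
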